From historical data on pregnancies at ChristianaCare Health System, we estimated a historical preterm birth rate of 9.1%. The sample size estimation is based on simulations of co-primary outcomes based on a simulated distribution of gestational age with a singleton preterm birth rate of 9.1%, and an effect of intervention based on literature data²⁶⁻²⁸, with α -level spending of 0.05 shared between co-primaries using Holm's method.

Given shut-down of the study due to the SARS-CoV-2 pandemic, the sample size for the study is estimated to be approximately 1,453 subjects in the prospective arm, and approximately 10,000 in the historical control group. In the primary and alternative analyses, more than 10,000 subjects may meet the eligibility criteria for the historical control group and have the required data, and if so, they will be included in the study.

Power and sample size for this study are affected by factors including the proportion of prospective subjects receiving PreTRM® risk scores at or above the threshold of 16% risk (the study Screen Positive Rate (SPR)), the proportion of higher-risk subjects complying with interventions (compliance), and the rate at which subjects and their neonates remain in the study (retention). For the purpose of power and sample size estimation and based on study monitoring, we estimate that 34% of subjects in the pre-pandemic portion of the prospective arm had PreTRM® risk scores at or above the threshold of 16% risk (the SPR).

Power and sample size are also affected by the study population's baseline level of risk of adverse neonatal outcomes related to prematurity, the sensitivity of testing in identifying at-risk pregnancies, retention of subjects in the study and the efficacy of the interventions as implemented in the study. Literature²⁶⁻²⁸ indicates that the effect of treatment is not constant across different values of GAB. Thus, there is no single value of the effect size in terms of proportion of subjects with NMI less than 3, or mean length of stay. Rather, the effect size is larger for subjects with earlier GAB, while the effect size is reduced for subjects with later GAB.

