For these reasons, power and sample size were estimated based on simulations, using a range of possible values for the factors noted above. These simulations used the observed distribution of GAB from previous studies, adjusted to match the expected overall preterm birth rate of 9.1% in this study. Treatment effect was modeled as a shift in the GAB corresponding to the effect sizes reported in published studies of preterm birth prevention that were based on single treatment modalities, and with extrapolated treatment effects estimating additive effects of bundled interventions.

For the first co-primary endpoint, reduction of severe composite morbidity/mortality, a range of the possible expected effect size can be inferred from the simulations. In the simulations, the proportion of subjects with NMI ≥ 3 is expected to be between 0.023 and 0.02 in the prospective arm and near 0.036 in the control arm based on a previous clinical utility study (Sera Prognostics: data on file). Assuming these proportions, a one-

sided Fisher's Exact test, a sample size of approximately 1,453 subjects with outcomes in the prospective arm with 55% compliance among higher risk subjects and about 10,000 historical controls provides power of 0.7 – 0.9 (NCSS PASS 2020, module "Group-Sequential Tests for Two Proportions").

For the second co-primary test, length of neonatal hospital length of stay from time of birth up to neonatal discharge is assessed by Cox proportional hazards regression with stratification. The hazard ratio based on simulations is expected to be between 1.32 and 1.46 based on a previous clinical utility study (Sera Prognostics: data on file). Assuming these hazard ratios, a sample size of approximately 1,453 subjects with outcomes in the prospective arm with 55% compliance among higher risk subjects and about 10,000 historical controls provides power of 0.8 – 1.0 (NCSS PASS 2020, modules "Group-Sequential Tests for Two Hazard Rates" and "Tests for Two Survival Curves Using Cox's Proportional Hazards Model"). Stratification is indicated based on non-proportionality observed in previous studies.

The two co-primary endpoints provide independent measurements of improved neonatal outcomes. Due to their correlation, there may be modest power to be gained from having two co-primary endpoints. The estimated study power for the combination of the two co-primary endpoints is 0.8 – 1.0.

5 Statistical Analysis

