5.1 Analysis Populations

One control population will be considered in primary analyses: the historical control population. The historical control population includes all subjects who attended ChristianaCare during the eligibility period and who satisfy all eligibility criteria.

The historical control arm will be the control population for primary and alternative analysis of the primary, secondary and exploratory endpoints.

Seven subject populations will be considered in the analyses: an Intent-to-Treat (ITT) population, a modified ITT population, a completer(s) population, a compliant completers population, a non-intervention completers population and a safety population. The completers, compliant completers, non-intervention completers and modified ITT populations are subsets of the ITT population.

The ITT population includes all historical subjects selected and all prospective patients enrolled regardless of whether or not the co-primary outcomes were observed, or in the prospective arm, any PreTRM test result has been generated or intervention consent has been signed. Subjects with missing outcomes will be handled as described in the missing data sensitivity analyses.

The modified ITT (mITT) population includes all subjects for whom both co-primary outcomes are known; and who have either been selected for the historical control group, received a not-higher-risk PreTRM® test result, or consented to and initiated treatment before 24^{0/7} weeks gestation after receiving a higher risk PreTRM® test result.

The completers population includes subjects for whom both of the co-primary outcomes are known, and, in the prospective arm, for whom a PreTRM® test result was generated.

The compliant completers population includes ITT subjects who have missed no more than 20% of daily doses for both low-dose aspirin and vaginal progesterone, and participated in weekly care management calls with no more than 20% missed weeks.

The non-intervention completers population includes all ITT subjects who received a higher-risk PreTRM® test result but neither consented to nor initiated treatment before 24^{0/7} weeks gestation.

The safety population includes all eligible subjects who gave consent to participate in the study and attempted a blood draw for the PreTRM® test, regardless of receipt of study interventions.

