Sensitivity analyses will be performed to check uncertainties in our analysis, as well as address basic assumption validation and the effect of unmeasured/unbalanced confounding factors on primary outcomes. The analyses will compare inclusion and omission of covariates in the analyses of primary, secondary and exploratory endpoints in the mITT population. As PTB is an outcome whose consequences are dominated by the lower tail of the gestational age distribution, sensitivity analyses will also examine the effect on effect size estimates of omitting outliers from the analyses.

A sensitivity analysis to control for reduction in subject number in the prospective arm of the mITT population will be performed. The primary and alternative analyses will be replicated as sensitivity analysis with bootstrap sampling of historical controls to the same number of subjects as the prospective arm. If exclusion of any completers from the mITT population is significantly associated with variables specified for the alternative analysis, this analysis will be repeated with such variables included as covariates. Subjects with missing data for required variables will be excluded from the covariate analysis.

A Bayesian Meta-Analysis will be performed on the data from this study and relevant previous studies. This will be described in a separate document.

Health Economic Outcomes:

Total cost of hospital care for each of the mother and neonate beginning at initiation of care through primary delivery and a gestational age of 40^{0/7} weeks in prospective vs. historical subjects. Analysis of these outcomes is covered in a separate SAP entitled SEAR.

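### Down-sampling the historical controls cannot show what removing higher-risk non-starters from the mITT prospective arm does to the estimate; it mainly costs precision

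*SAP*

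**What the plan says.** The purpose is given in Section 5.7: "A sensitivity analysis to control for reduction in subject number in the prospective arm of the mITT population will be performed". The method follows at once: the primary and alternative analyses are "replicated as sensitivity analysis with bootstrap sampling of historical controls to the same number of subjects as the prospective arm". A conditional step comes next: "If exclusion of any completers from the mITT population is significantly associated with variables specified for the alternative analysis", then "this analysis will be repeated with such variables included as covariates".

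Section 5.1 defines who is lost. Both co-primary outcomes must be known in either arm. A prospective woman with a higher-risk result must also have "consented to and initiated treatment before 24^{0/7} weeks gestation after receiving a higher risk PreTRM® test result". No such condition applies to a woman with a not-higher-risk result or to a control.

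Section 4 gives the planning inputs: "approximately 1,453 subjects in the prospective arm, and approximately 10,000 in the historical control group"; "34% of subjects in the pre-pandemic portion of the prospective arm had PreTRM® risk scores at or above the threshold of 16% risk"; and power computed "with 55% compliance among higher risk subjects".

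Section 6.1 concedes that incomplete acceptance among higher-risk women is a bias that cannot be directly adjusted, because controls have no PreTRM-defined risk group. Elsewhere in Section 5.7, exploratory replications use the ITT population and the completers population, the latter with treatment covariates.

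**The concern.** Unequal arm sizes do not bias a comparison. The smaller prospective arm matters because of which women were removed: they all come from the group the test labels as higher risk, and nothing comparable is removed from the controls. Resampling the controls at random to a smaller number keeps their expected outcome rate, so it cannot respond to that selection. Agreement with the primary result would be expected whatever the exclusions had done, and a loss of significance could simply reflect the discarded controls. Neither result would tell the reader whether the mITT exclusions matter, although this is the only analysis the SAP ties explicitly to the reduced mITT arm.

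**Working it through.** **1. Reproducing the SAP's power.** Inputs from Section 4: NMI of 3 or more at 0.036 in controls and 0.023 to 0.02 in the prospective arm; one-sided Fisher's exact test; 0.05 shared by Holm's method, so 0.025 at the first step. With 1,453 × (1 − 0.34 × 0.45) = 1,231 prospective women and 10,000 controls, exact power is 0.68 to 0.88, which rounds to the stated 0.7 to 0.9. With all 1,453 it is 0.75 to 0.93. The match supports reading 1,453 as the count before exclusion and 55% as the share starting treatment.

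**2. Who is removed.** Higher-risk: 1,453 × 0.34 = 494. Not starting: 494 × 0.45 = 222, or 15.3% of the arm. Higher-risk share afterwards: (0.34 × 0.55) / (0.66 + 0.34 × 0.55) = 0.187 / 0.847 = 22.1%. The two percentages do not depend on whether 1,453 is counted before or after exclusion.

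**3. Effect on the estimate with no treatment effect.** Let r be the ratio of NMI ≥3 risk, higher-risk to not-higher-risk. The SAP does not give it, so 1.5 to 4 is an assumed range. Fix the whole-population rate at 0.036:

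- p_low = 0.036 / (0.66 + 0.34r), and p_high = r × p_low
- p_mITT = (0.66 × p_low + 0.187 × k × p_high) / 0.847, and RR = p_mITT / 0.036

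Here k is the risk of starters relative to all higher-risk women. If starting is unrelated to outcome, k = 1. As an alternative, suppose 60% of higher-risk women accept at 0.63 and 40% at 0.43 (0.6 × 0.63 + 0.4 × 0.43 = 0.55), and the latter have 1.5 times the risk. Then k = [(0.378 + 0.172 × 1.5) / 0.55] / (0.6 + 0.4 × 1.5) = 1.156 / 1.2 = 0.964.

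| r | RR, k = 1 | RR, k = 0.964 |
|---|---|---|
| 1.5 | 0.95 | 0.94 |
| 2 | 0.91 | 0.90 |
| 3 | 0.86 | 0.84 |
| 4 | 0.82 | 0.81 |

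The number of controls does not enter these formulas. In 4,000 simulated trials at r = 2 with k = 1, the mean odds ratio was 0.907 with 10,000 controls and 0.907 after resampling them to the size of the mITT arm; at r = 3 it was 0.852 and 0.855.

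**4. Effect on precision.** Var(log RR) = (1 − p₁)/(n₁p₁) + (1 − p₀)/(n₀p₀). At r = 2 and k = 1, p₁ = 0.0328:

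- Prospective term: 0.9672 / (1,231 × 0.0328) = 0.0240
- Control term, 10,000 women: 0.964 / 360 = 0.0027, so SE = √0.0267 = 0.163
- Control term, 1,231 women: 0.964 / 44.3 = 0.0218, so SE = √0.0458 = 0.214

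The ratio is 1.31, and over r = 1 to 4 it is 1.29 to 1.33. At the planned effects, exact power at one-sided 0.025 falls from 0.68–0.88 to 0.44–0.64.

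**5. What would respond to the exclusions.** Restoring the removed women returns the higher-risk share to 34%. With no treatment effect the expected rate is then 0.66 × p_low + 0.34 × p_high = 0.036, so RR = 1 at every r.

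**The case against.** Several counter-arguments have force.

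- **The covariate repeat.** A reader might infer that the whole sensitivity analysis leaves every bias in place and can only agree with the primary result. The text does not support that. The primary model in Section 5.3 has three candidate covariates and the alternative list has fifteen, so the repeat can add variables to the primary model and move the estimate. It is still a weak safeguard: it depends on a significance test, its variables are already candidates for the alternative analysis's propensity weights, and it cannot use the PreTRM score, on which Section 6.2 says self-selection depends.
- **The stated aim is number, not bias.** That is literally so, but number alone needs no control, and the trigger for the repeat is an association between exclusion and baseline variables.
- **Other analyses exist.** The ITT and completers replications do bring the women back, so the SAP is not without a remedy. They are exploratory and are not named as the check on the mITT exclusions.
- **The estimate need not stay exactly fixed.** The check above is unadjusted and binary. In the weighted analysis, moving from about 8:1 to 1:1 changes the population to which results are standardised. If the top quantile of hospital stay is defined on pooled data, which the SAP does not settle, the cut-off shifts too. These shifts come from the arm mix and would not measure the effect of the exclusions.
- **Precision.** The 30% applies to a single down-sampled set. The SAP does not say whether draws are repeated and summarised, and averaging many draws would simply approach the full-control result. The analysis carries no alpha, so the power loss affects only its interpretation.

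**Conclusion.** The resampling step does not do what the analysis is introduced to do. It leaves the expected estimate essentially unchanged, including any distortion from removing higher-risk non-starters, and a single draw raises the standard error by about 30%. The covariate repeat helps only through measured baseline variables.

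The possible distortion, an RR of about 0.94 to 0.81 with no treatment effect, rests on assumed outcome ratios of 1.5 to 4 and modest selection among accepters, on 55% compliance meaning the share starting treatment, and on ignoring removals for unknown outcomes. A reader could reach a larger figure by assuming that 75% of events fall in the higher-risk group (ratio about 5.8, RR about 0.77), but the SAP gives no such detection rate. Nor does it say that agreement of this analysis would be presented as proof that the exclusions were harmless.

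Severity is minor: one sensitivity analysis is badly matched to its purpose, and better-suited analyses already sit in the same section.

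**What to change.** Delete the down-sampling and keep all historical controls. Name the ITT replication, or a completers replication run without the treatment covariates, as the sensitivity analysis for the mITT exclusions. State that it uses the same pre-pandemic cut-off as the primary analysis, because Section 5.1 defines ITT as all women enrolled while Section 4 restricts the primary analysis. For the confidence interval, bootstrap both arms at their own sizes.

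As a supplement, weight each treated higher-risk woman by the inverse of her modelled probability of starting treatment, fitted among all tested higher-risk women on baseline covariates plus PreTRM score. The SAP should state that this assumes acceptance is explained by those measured variables, and that it targets the effect had all higher-risk women started treatment, which is a different question from the strategy as taken up.

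The cost is a few sentences in Section 5.7 and, for the supplement, one further model. The change itself calls for no new data collection.

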5.8 Safety Analyses

Drawing of blood and the interventions planned for women diagnosed as higher risk have a known and established safety record. However, we will collect and analyze safety information for the mother. The definitions for AEs, UAEs, and SAEs are included in the protocol. These adverse events will be summarized and descriptive statistics provided. All adverse events (AEs) will be coded using the Medical Dictionary for Regulatory Activities(MedDRA). Frequencies of adverse events will be presented by system organ class, preferred term, treatment group, and severity level. Safety analyses will be performed in the safety population.

5.9 Subgroup analyses

Subgroup analyses may be performed if the sample size in this study can provide sufficient power.

The use of regression methods simplifies analysis of subgroups, or the impact of other factors such as age, or other comorbidities on the effectiveness of the PreTRM® strategy. These can easily be included as covariates in a regression model, including treatment (prospective arm or historical control) by covariate interactions. All covariates included in the alternative analysis in the Covariate Analyses section will be included in subgroup analyses.

In prespecified subgroup analyses, interaction terms will include age, chronic hypertension and gestational diabetes. Covariates categorical BMI, categorical parity and

insurance status will be used to define subgroups. The remaining covariates defined for the alternative analysis will be used as covariates in these analyses.

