5.3 Covariate Analyses

The prospective participants and historical controls in the study may differ in ways other than the interventions or exposures under investigation. Covariates will be used to adjust the regressions prespecified in the primary analysis for potential differences between the control and prospective arms, and in derivation of propensity scores used to adjust for biases between the two arms, either by weighting subjects in the alternative analysis or by matching subjects in exploratory analyses..

The following variables are candidates for inclusion as covariates in the primary analysis: regression with covariates. These baseline covariates are present before blood draw.

- Maternal age
- Categorical parity: multiparous vs. nulliparous
- Maternal substance use disorders assessed as Neonatal Opioid Withdrawal Syndrome

The following variables are candidates for inclusion as covariates in the alternative analysis using inverse probability score weighting, and in the exploratory analysis using propensity matching. These baseline covariates are present before blood draw.

- Maternal age
- Categorical parity (nulliparous vs. multiparous)
- Gravidity (integer)
- Number of term children
- Number of miscarriages
- Maternal race
- Pre-pregnancy continuous BMI
- Pre-pregnancy categorical low BMI<19
- Maternal height
- Maternal chronic hypertension
- Gestational diabetes
- Insurance status
- Smoking status
- Maternal substance use disorders assessed as Neonatal Opioid Withdrawal Syndrome
- Delivery outside of ChristianaCare

Inclusion of covariates in the covariate-adjusted primary, alternative and exploratory analyses will depend on the proportion of missing values for the covariate, as follows. For each candidate variable, if fewer than 1% of subjects have a missing value, that variable will be included as a covariate in the analysis. Sensitivity of results to missing data will be examined using missing data analysis methods.

The primary and alternative analyses will use cases with complete data for the included covariates, provided that no more than 5% of the total subjects are excluded from the analysis. If more than 5% of the total subjects would be excluded from the analysis,

candidate variables will be dropped from the analyses in order of the percent missing, until no more than 5% of the total subjects are excluded from the analysis.

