The propensity score model will be derived from logistic regression using the key clinical covariates available at the gestational age of PreTRM® blood draw in the historical cohort, as well basic demographic characteristics. The variables used to generate propensity scores are specified above.

The performance of the propensity score model will be evaluated by AUC/ROC c-index; potential interaction terms or high degree of terms may be included to improve the performance of the propensity model. We will obtain an estimation for the propensity score: predicted probability (p).

With propensity score methods, we will check whether covariates are balanced across the prospective and historical cohorts. We can examine the distribution of propensity score between groups. We will assess covariate balance between groups using p-value for comparison of two group, as well absolute standardized mean difference (ASMD), with an ASMD <0.1 indicating good balance.

We propose Inverse Propensity score Weighting (IPW) method for the alternative analysis. IPW is a statistical technique for calculating statistics standardized to a pseudo-population different from that in which the data was collected. After obtaining propensity score, we define for the prospective arm:

$$IPW = \frac{1}{PS}; \quad IPW = \frac{1}{PS}; \quad \text{for historical controls: } IPW = \frac{1}{1-PS}.$$

$IPW = \frac{1}{1-PS}$. To avoid the IPW method's instability to extremes of propensity among participants with high propensity score weights with undue influence the results, we will use truncated scores and weights: 1) below the 1st or 5th percentile and above the

99th or 95th percentile; resulting in weights between reasonable intervals for all participants; 2) truncating propensity score <0.001 or >0.999.

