- a) The higher-risk group will be compared to the not-higher-risk group within the prospective arm, for tests of equivalence. This comparison is independent of any selection biases or epoch effects present in comparisons of the prospective arm relative to historical controls.
- b) The not-higher-risk group of the prospective arm will be compared to historical controls to assess test sensitivity. It is expected that there will be significant differences in baseline characteristics between the two groups. The analysis will be performed without adjustment, adjusted for covariates specified for the primary analysis, and adjusted via propensity scoring as specified for the alternative analysis.
- c) The higher-risk group in the prospective arm will be compared to a control comparator group estimated as the difference between the control group and the not-higher-risk group, to assess efficacy of the intervention strategy. For count endpoints, direct subtraction of counts (adjusted for arm size) will be used to estimate the comparator group. For non-count endpoints, a number of most similar outcomes proportional to arm size will be removed from the control comparator group for each subject in the not-higher-risk group. It is expected that there will be significant differences in baseline characteristics between the two groups. The analysis will be performed without adjustment, adjusted for covariates specified for the primary analysis, and adjusted via propensity scoring as specified for the alternative analysis.

The following exploratory outcomes will be examined using only the descriptive statistics described above.

- Birthweight
- Number of days of mechanical ventilation

- Amount of surfactant administered
- Occurrence of birthweight <1500g and <2500g
- Individual components of composite morbidity/mortality index
- Whether or not a neonate received surfactant
- Occurrence of pneumonia
- Occurrence of 5-minute Apgar<7
- Occurrence of asphyxia
- Occurrence of preeclampsia
- Occurrence of gestational diabetes mellitus
- Rate of PPROM
- Rate of preterm delivery not associated with PPROM
- Baseline and on-treatment progesterone levels determined by LC-MS

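### Gestational diabetes has no date limit in the SAP, yet serves as a pre-draw covariate for weighting and matching, as an interaction term, and as an outcome

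*SAP*

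**What the plan says.** Gestational diabetes appears in three roles.

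- **Weighting and matching covariate (SAP 5.3).** "Gestational diabetes" is an entry, with no date or gestational-age limit, among the "candidates for inclusion as covariates in the alternative analysis using inverse probability score weighting, and in the exploratory analysis using propensity matching". The SAP says of this list: "These baseline covariates are present before blood draw". The same section later describes the propensity model as using "key clinical covariates available at the gestational age of PreTRM® blood draw in the historical cohort".
- **Interaction term (SAP 5.9).** Regression models may be extended, "including treatment (prospective arm or historical control) by covariate interactions", and in the prespecified subgroup analyses "interaction terms will include age, chronic hypertension and gestational diabetes". Every covariate of the alternative analysis is also carried into the subgroup models.
- **Outcome (SAP 5.7).** "Occurrence of gestational diabetes mellitus" stands on a list introduced by "The following exploratory outcomes will be examined using only the descriptive statistics described above".

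Three conditions limit the reach. A candidate covariate enters only if fewer than 1% of subjects lack a value (5.3). Subgroup analyses are optional and depend on power (5.9). The primary-analysis covariates are maternal age, parity and a substance-use proxy, so gestational diabetes is not among them (5.3).

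**The concern.** The outcome list implies that cases are expected during the study, while the covariate list treats the same condition as settled before the draw at 19 1/7 to 20 6/7 weeks. With no date rule, a programmer could code any diagnosis in the pregnancy record and reasonably believe the SAP had been followed.

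Two things would then go wrong. First, the variable could be affected by what follows the test, since the interventions and the added contact might change how often the condition occurs or is found. Weighting or matching on it would then be adjustment for a post-test variable. Second, a woman who delivers before diagnosis can only be coded as not having the condition, so the earliest births, which carry the worst neonatal outcomes, would all fall in one stratum. If the strategy works better at early gestational ages, the two strata would show different effects even though gestational diabetes modifies nothing. SAP Section 4 itself expects a larger effect at earlier gestational age at birth.

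**Working it through.** **Textual check.** No figure in the SAP depends on this point, so the main check sets the sections side by side. Section 5.3 gives the list a pre-draw status but the entry no cut-off. Section 5.7 treats the condition as something that occurs. Section 5.9 takes the variable over with no further definition. The status sentence cannot be relied on to filter late diagnoses, because the same list contains Neonatal Opioid Withdrawal Syndrome and delivery outside ChristianaCare, which are known only at or after delivery.

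**Size: inputs.** From SAP Section 4: control rate of NMI ≥3 of 0.036; 1,453 prospective subjects; about 10,000 controls. Assumed, because the SAP gives none of them: recorded prevalence *g* of 8% among women undelivered at diagnosis (5% or 12% as alternatives in the prospective arm); a share *E* of women who deliver before diagnosis, all with NMI ≥3; and a risk ratio *k* of 1 to 2.5 for NMI ≥3 with gestational diabetes. Among later births the risk is r = (0.036 − E)/(1 − E).

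**A. Weighted main effect**, weighting on gestational diabetes alone, true risk ratio 1.00. In each arm:

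- b = r/(1 − g + g·k)
- share with a recorded diagnosis: pG = (1 − E)·g
- risk with it: k·b
- risk without it: [E + (1 − E)(1 − g)·b]/(1 − pG)

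Both arms are standardised to the pooled share P = (10,000·pG(control) + 1,453·pG(prospective))/11,453.

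Example with E = 0.005, k = 2.5, g = 8% (control) and 12% (prospective): r = 0.03116; b = 0.02782 and 0.02640; risk with the diagnosis 0.0695 and 0.0660; risk without 0.0331 and 0.0319; P = 0.0846.

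- Control: 0.0846 × 0.0695 + 0.9154 × 0.0331 = 0.0362
- Prospective: 0.0846 × 0.0660 + 0.9154 × 0.0319 = 0.0348
- Weighted risk ratio: 0.962

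With 8% against 5% and the same E and k, the weighted risks are 0.0359 and 0.0370, ratio 1.032. Over E = 0.005 and 0.01 and k = 1, 1.5 and 2.5, the range is 0.96 to 1.03. A true ratio of 0.64 (0.023/0.036, the SAP's smaller effect) becomes about 0.62 to 0.66. With 8% in both arms the ratio is unchanged.

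**B. Interaction**, k = 1, g = 8% in both arms. The strategy halves the earliest births and does nothing else, equally in all women. With the condition, the risk is r in both arms, so the odds ratio is 1.00. Without it, the risk is [E + (1 − E)·0.92·r]/[E + (1 − E)·0.92], with E halved in the prospective arm and r unchanged.

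For E = 0.010: r = 0.026/0.990 = 0.02626.

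- Control: (0.0100 + 0.0239)/0.9208 = 0.0368
- Prospective: (0.0050 + 0.0240)/0.9204 = 0.0316
- Odds ratio: 0.85

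The standard error of the log interaction is the square root of the summed reciprocals of the eight expected cell counts. Expected events with the condition are 1,453 × 0.995 × 0.08 × 0.02626 = 3.0 (prospective) and 10,000 × 0.990 × 0.08 × 0.02626 = 20.8 (control). Without it they are 42.2 and 339.2. This gives 0.64, so the shift is −ln(0.852)/0.644 = 0.160/0.644 = 0.25 standard errors.

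| E | Share of NMI ≥3 (E/0.036) | Odds ratio without / with | Standard error | Shift (standard errors) | Rejection, two-sided 5% |
|---|---|---|---|---|---|
| 0.3% | 8% | 0.96 / 1.00 | 0.58 | 0.08 | 5.1% |
| 0.6% | 17% | 0.91 / 1.00 | 0.60 | 0.16 | 5.3% |
| 1.0% | 28% | 0.85 / 1.00 | 0.64 | 0.25 | 5.7% |

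A milder gradient (30% reduction of early events, 10% of later ones) gives 0.84 to 0.88 against 0.90, a shift of at most 0.10 standard errors. A constant 30% reduction gives no spurious interaction.

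**The case against.** The strongest reply is that the SAP does state the timing. Section 5.3 says twice that these covariates are those known by the draw, and 5.9 draws on that list. Status known at the draw and occurrence over the pregnancy can be two separate variables, so the three roles are not in themselves contradictory. If the stated timing is followed, the mechanism disappears, because every eligible woman is still pregnant at the draw. This stands to the extent that a reader may not infer that the analyses certainly use post-test diagnoses: the SAP gives no timing of diagnosis. It does not remove the point, because nothing in the definition enforces the timing and other entries on the list plainly break it.

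A reader might also infer that a false interaction would be reported. The point odds ratios suggest it, but with about 3 to 4 expected prospective events among women with the condition, the bias would be lost in the noise, and the subgroup analyses may never be run. The scenario also rests on outside assumptions and on NMI split at 3, whereas Section 5.5 specifies a weighted ordinal model.

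A reader might further infer that weighting balances away an effect of the strategy on gestational diabetes itself. The SAP does not support this: Section 5.7 only describes that outcome, so its specified analysis is neither weighted nor matched.

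Finally, Section 5.4 compares four adjustment methods and 5.7 compares results with and without covariates. These offer some protection, but neither check would identify a covariate's timing as the cause of a discrepancy.

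**Conclusion.** The point holds as a defect of definition. One undated variable is used as a pre-draw covariate, as an arm-by-covariate interaction and as an outcome, and the SAP does not say which diagnoses count for which use. The exposed analyses are the inverse-probability-weighted alternative analysis, the propensity-matched analysis and the optional subgroup analyses. The primary covariate regression is untouched.

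The likely harm is small: a null weighted risk ratio moves to about 0.96 to 1.03, and only if recorded prevalence differs between arms; the interaction is biased by at most about 0.25 standard errors. Both figures rest on assumed prevalence, early-birth share and effect pattern, and calculation A also on an assumed risk ratio. Calculation A weights on this one variable alone. Neither figure supports a claim that a reported conclusion would change. The reason to act is that the correction is nearly free and keeps possible post-test information out of analyses meant to adjust for baseline differences.

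**What to change.** In Sections 5.3 and 5.9, restrict the covariate and the interaction term to diabetes diagnosed before the blood draw and, for controls, who had no draw, before the same gestational age. If diagnosis dates are not available in both cohorts, drop gestational diabetes from the weighting and matching list and from the interaction terms. In either case keep its occurrence only as the descriptive outcome in Section 5.7.

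Pre-existing diabetes mellitus could replace it only if it is dated before the draw and meets the 1% missingness rule. Section 5.2 names it only for descriptive tables, so neither condition can be assumed.

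The cost is a change of wording plus a check that diagnosis dates exist in the historical data. The downside is slightly less adjustment for metabolic risk first recognised later in pregnancy.
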